## HYPOTHESES AND OBJECTIVES

### Overall objective

- To determine the impact in terms of functional recovery, return to pre-hip fracture functional status, of elderly patients treated with the new multimodal therapeutic exercise programme and follow-up for one year compared to patients treated with the previously developed standardised nursing care plan at the Hospital San Juan de Dios de León.

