### Hypothesis

A multimodal functional recovery programme of therapeutic exercise with patient follow-up after hip fracture surgery in older people can achieve better results than standard practice (standardised nursing care plan) in terms of recovery of functional status prior to hip fracture.

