#### **First group: variables established in the National Hip Fracture Registry, defined according to its protocol**

These scales will be administered to both groups:

- Cohort of unexposed patients: to be administered on the dates indicated.

- Cohort of exposed patients (retrospective): data will be retrieved from the Exceldata collection system that the medical management of the HSJD manages for the follow-up of these patients and the report to the national hip fracture registry.

These variables include socio-demographic, clinical and functional characteristics prior to surgery (Table I):

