Gait is the parameter most strongly associated with frailty states, with gait speed being the parameter most commonly associated with frailty(34,36). This is why it is so important to recover functions and capacities in this area of movement. This scale is very easy to use and apply and is used by the national fracture registry, which allows us to make comparisons and statistical analyses with the results published with this registry.

It assesses by ability levels ranging from 0 to 11. Its design allows firstly to determine gait ability and secondly to see the evolution and establish treatment guidelines.

Capacity levels:

- Level 1-Independent mobility inside and outside the home without technical aids
- Level 2- Independent mobility inside and outside the home, with technical assistance.
- Level 3- Independent mobility inside and outside the home with two technical aids or walker.
- Level 4- Independent mobility only indoors without technical assistance.
- Level 5- Independent mobility only indoors with a technical aid.
- Level 6- Independent mobility only indoors with two technical aids or walker.
- Level 7- Independent mobility only within the house under personal supervision.
- Level 8- Mobility only within the home with little assistance from a person.
- Level 9- Mobility only within the home with a lot of help from a person.
- Level 10- Mobility with two people or no mobility.
- Level 11- Unknown.

For simplicity this variable is summarised in these questions:

- Technical aids (yes/no).
- Outside/inside the home.
- And note the best situation, i.e. it is better with a cane outside than without help at home.

This scale is administered at admission, 6 weeks, 4 months and 1 year.

• ***ModifiedFunctionalAmbulatoryClassifier(mFAC)(36).***

It is a scale that assesses different levels of ability by grading them between 0 and 6. Its design allows firstly to determine gait ability and secondly to see the evolution and establish treatment guidelines. The modified gait assessment scale has shown an intraclass correlation coefficient(ICC)= 0.960, with a 95% confidence interval: 0.942-0.972, an inter-observer agreement Cohen's kappa index of 0.83 (CI: 0.69-0.97) and a validity p= 0.814 (36-38)

The capacity levels for this scale are:

- Level 0: Patient who cannot remain seated for more than 1 minute without the help of the backrest and armrest.
- Level 1: Patient who can remain seated without the aid of the backrest and armrest for more than 1 minute.

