**Table III. Summary of variables, assessment instruments and collection period**

Variable	Questionnaire	Time of administration
March Capacity	RNFC scale	Entry, at 6 weeks, 4 months and 1 year.
	The walking capacity assessment scale (mFAC).	Entry, at 6 weeks, 4 months and 1 year.
Physical capacity	Barthel Index	At 6 weeks, 4 months and 1 year.
	Oxford Hip Score Scale	At the 1st, 3rd, 6th and 12th month.
Sarcopenia	SARC-F Scale	At 6 weeks, 4 months and 1 year.
Adverse Events	STRATIFY scale	At 6 weeks, 4 months and 1 year.
	Medical complications (ad hoc questionnaires)	At 6 weeks, 4 months and 1 year.
Quality of life	Questionnaire EQ-5D-5L	At the 1st, 3rd, 6th and 12th month.

- The functional recovery programme designed and implemented as standard practice from 1 January 2021. This programme consists of a series of presentations and videos, in simple language with information and recommendations. It will provide answers to patients' most frequently asked questions and will also allow patients to receive reminders regarding their care (recommended exercises, precautions to take in certain circumstances, alerts, etc.).

It is the clinician and the patient, or family member if applicable, who enters the data directly into the application, prior to accepting the legal clauses to that effect.

The study variables collected in the project are included among the clinical variables included in the orthogeriatric protocol for the care of hip fracture patients at the HSJD. In order to analyse those established for this study, the variables will be extracted from the data collection platform, the PI being responsible for the storage and processing of the data in accordance with current legislation.

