This programme is divided into 5 phases, each of these phases coincides with a level of the gait assessment scale. Each individual will start at the level assigned by the doctor and will only have access to the videos of the indicated level and the levels below it. As the patient meets the recovery goals, the physician will provide access to the higher level videos. The functional recovery plan begins the day after the hip fracture and continues after the patient has been discharged for a total of 16 weeks.

- The therapeutic plan for the historical control group (standard practice until 31 December 2020) consisting of postural changes described in the standardised nursing care plan. Within this plan, the patient was moved to a sitting position prematurely (within the first 24 hours) and started to ambulate within the following 48

hours, provided that the patient's general condition allowed it. This group did not receive any specific functional recovery plan.

- The patient is discharged from hospital and will be assigned a link where he/she will be able to access the online platform to send information from the questionnaires sent during the established periods of 1, 3, 6 and 12 months and will also be sent videos illustrating the rehabilitation exercises that he/she will have to perform during this period. The patient and/or carer will be explained how the tool works, how to access the digital information content and how to access the questionnaires. A means of contact will be provided to resolve doubts, if any. The PI will have access through the web/app platform to a control panel where he/she will be able to detect a patient's lack of adherence, if any, or alerts related to clinical evolution, allowing for exhaustive monitoring of the patient.
- Analysis of results: The data collected will be analysed with the SPSS programme. The mean, median and standard deviation of each of the variables will be calculated. Based on the data obtained from the existing literature(31), having selected a sample of 67 patients, a normal distribution can be assumed for all variables  
For baseline demographic and clinical characteristics, a comparison of means for quantitative variables (t-Student), and of proportions (Chi-square) for qualitative will be performed  
The statistical analysis will be carried out with a confidence level of 95%, so that statistically significant values will be considered to be those whose probability is < 0.05.

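### No primary scale, definition of recovery or visit is named and every p < 0.05 counts as significant: up to six tests of one hypothesis give about a 26% chance of a false difference and 14% of a false benefit, if independent and two-sided.

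*Combined protocol and SAP*

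**What the plan says.** **Decision rule.** In the work plan, under Description of the process (Analysis of results), the protocol states "The statistical analysis will be carried out with a confidence level of 95" per cent, and that "statistically significant values will be considered to be those whose probability is < 0.05". It gives no adjustment, no hierarchy and no order of testing. The t-test and chi-square test named there are for baseline characteristics; no test is named for any outcome.

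**Hypothesis.** There is one: that the programme "can achieve better results than standard practice (standardised nursing care plan) in terms of recovery of functional status" prior to the fracture. The Overall objective is similar: "To determine the impact in terms of functional recovery, return to pre-hip fracture functional status". Neither ties recovery to a scale, a threshold or a visit.

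**Scales and visits.** RNFC and mFAC both measure walking ability. For each, the text says "This scale is administered at admission, 6 weeks, 4 months and 1 year", and Table III repeats the schedule: "Entry, at 6 weeks, 4 months and 1 year".

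**Which cohorts have the data.** The First group section, which covers RNFC and mFAC, says "These scales will be administered to both groups", with the 2020 values taken from existing hospital records. The Variables section says follow-up under the earlier system ended after one month. The Second group section says its variables are measurable only in the 2021 cohort, and Table II under that heading lists RNFC and mFAC again.

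**The concern.** A 95% confidence level suggests a 5% error rate for the study's conclusion. That holds if one test decides. Here one idea, recovery of function, could be supported by either of two scales at any of three visits, and each result would be called significant on its own. The scale, the visit and the definition of recovery can all be chosen after the data are seen.

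The protocol plans journal articles and congress presentations. A reader of those reports could not tell a planned comparison from the most favourable of several.

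**Working it through.** **Inputs**
- Per-test threshold: 0.05 (Analysis of results). Sidedness is not stated; two-sided is assumed.
- Scales: 2 (RNFC, mFAC). Post-baseline visits: 3 (6 weeks, 4 months, 1 year; Table III).
- Largest number of between-cohort tests the schedule allows: 2 × 3 = 6.
- Correlation between tests: not given. Independence, 0.5 and 0.8 (equal for every pair) are assumed.

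**The plan's own figure.** One test: 1 − 0.95 = 0.05 in either direction. A two-sided test puts half of that, 0.025, in the direction of benefit.

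**Six independent tests**
- At least one false difference, either direction: 1 − 0.95^6 = 0.265.
- At least one false benefit: 1 − 0.975^6 = 0.141.
- Upper bounds whatever the dependence: 6 × 0.05 = 0.30 and 6 × 0.025 = 0.15.

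**Correlation and fewer visits.** The tests use the same patients and related scales, so positive correlation is likely. The correlated rows are for jointly normal test statistics with equal correlation.

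| Tests | Correlation | Any false difference | False benefit |
|---|---|---|---|
| 1 | – | 5.0% | 2.5% |
| 2 (one visit) | 0 | 9.8% | 4.9% |
| 2 (one visit) | 0.8 | 7.8% | 3.9% |
| 4 (two visits) | 0 | 18.5% | 9.6% |
| 6 (three visits) | 0 | 26.5% | 14.1% |
| 6 (three visits) | 0.5 | 20.7% | 10.4% |
| 6 (three visits) | 0.8 | 13.9% | 6.9% |

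**Size relative to one test.** For false benefit, six tests give 14.1 / 2.5 = 5.6 times the single-test rate if independent, and 6.9 / 2.5 = 2.8 times at correlation 0.8. Two tests give 4.9 / 2.5 = 2.0 and 3.9 / 2.5 = 1.6 times.

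**How many tests are possible.** The First group section supports three visits in both cohorts. The Variables and Second group sections suggest that 2020 data at 4 months and 1 year, and perhaps at 6 weeks, may not exist. Six is therefore the most the schedule permits, not a count the protocol commits to.

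**The case against.** **The protocol never lists six tests, and never says that one significant result confirms the hypothesis.** This stands. The sentence on p < 0.05 only defines what will be called significant. A reader might infer a written rule that any one of six results proves the programme works; no sentence makes that link. The defect is that nothing limits or ranks the tests.

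**The 2020 cohort may have no data at the later visits.** This also stands, and it could cut the number of tests. With both scales at one visit, the rates fall to about 10% and 5%, still about double those for one test if the two are independent. If only one scale at one visit proves comparable, this source of inflation disappears, but the primary outcome would still be undefined.

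**The study is observational, with largely descriptive specific objectives.** This is partly right, and formal ordering of tests matters less for description. But the protocol also states a directional hypothesis and a significance threshold, so it should say which result bears on the hypothesis.

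**Conclusion.** The concern holds. No primary scale, definition of recovery or visit is named, and multiple testing is uncontrolled. With six independent two-sided tests, the chance of a false difference is about 26% and of a false benefit about 14%, against 5% and 2.5%. With correlations of 0.5 to 0.8, it is about 21% to 14% and 10% to 7%. With two tests, it is at most about 10% and 5%. Sidedness, the correlations and the number of tests are assumptions. The rates cover chance only, not bias from the historical comparison.

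Two further readings are not supported:
- A reader might take 26% as the chance of a false claim of benefit. That would need one-sided tests at 0.05, which the protocol does not state. Nor is 26% a strict ceiling for differences in either direction; the bound is 30%.
- A reader might conclude that the 2020 record certainly ends at one month, and that the confirmatory test belongs there. The sections conflict, so this is not established. One month also falls before the 16-week programme ends. The 2021 one-month contact is through the app, counted from discharge, while the 2020 values come from hospital records and the starting point of their month is not given. Neither timing nor mode of collection can be assumed to match.

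**What to change.** 1. Before any outcome data are examined, establish which post-surgery RNFC assessments the 2020 file holds, when they were made and how. Reconcile the Variables, First group and Second group sections accordingly.
2. In Analysis of results, name one primary outcome: return to pre-fracture RNFC level, at one visit that both cohorts have on a comparable schedule and mode of collection. RNFC is the natural choice because it is the registry's own scale and the 2020 data come from the registry collection. State the outcome test and test it two-sided at 0.05.
3. Test mFAC at the same visit, if recorded in both cohorts, only if the RNFC test is significant. This fixed order keeps the overall error rate for the two tests at 5%.
4. Report all other comparisons and all 2021-only results as estimates with 95% confidence intervals and no claim of significance.

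The cost is a check of the 2020 file and a few sentences in the protocol. The downside is that fewer results can be called significant. A Bonferroni split over six tests would also control the error rate (0.05 / 6 = 0.0083 per test; 1 − (1 − 0.0083)^6 = 4.9% if independent). But it would leave the primary outcome unnamed and would presume 2020 data that may not exist.

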## BUDGET

CONCEPT		COST (€)	AVAILABLE
Human resources	Translation service		NO
Material resources	Office supplies		NO
	Hard disk (2 units)	200	NO
	Laptop (2 units)		YES
Subtotal 1			2600
Dissemination costs	Publication of open access articles		NO
	Attendance at national congress (2 congresses: registration, travel and subsistence.		NO
	Attendance at international congress (2 congresses: registration, travel and per diem)		NO
Subtotal 2			3500
Other	Travel to centres		NO
	Acquisition of bibliography		NO
	SPSS License		NO
	Professional Office Package	100	NO
Subtotal 3			2400
TOTAL			8500 (€)

## INSTITUTIONAL LINKAGE

The project will be carried out at the HSJD and will be carried out by staff from the centre itself, staff from the Centro Universitario San Rafael Nebrija and the Research Department of the Fundación San Juan de Dios.

All three centres belong to the Order of St. John of God.

## DISSEMINATION PLAN

This project is relevant because of its impact at the clinical and care level and adds value through the implementation of the functional recovery programme using a technological medium.

It is intended to present the results of this study in high impact scientific publications related to geriatrics, orthopaedics and physiotherapy.

The presence at national congresses of traumatology, geriatrics and physiotherapy of the respective scientific societies is an objective within the dissemination plan.

## ANNEXES

**Annex I: Barthel Index Questionnaire (Spanish version) for the assessment of level of dependency.**

### BARTHEL INDEX

Patient's Name: .....	Date: .....
	Initial: .....
FEEDING	
10 = Independent. Able to apply any necessary device. Feeds in reasonable time.	.....
5 = Needs help (e.g; for cutting)	.....
BATHING	
5 = Independent	.....
PERSONAL TOILET	
5 = Independently washes face, combs hair, brushes teeth, shaves (manages plug, if electric)	.....
DRESSING	
10 = Independent. Ties shoes, fastens fasteners, applies braces.	.....
5 = Needs help, but does at least half of work in reasonable time.	.....
BOWELS	
10 = No accidents. Able to use enema or suppository, if needed	.....
5 = Occasional accidents or needs help with enema or suppository	.....
BLADDER	
10 = No accidents. Able to care for collecting device if used.	.....
5 = Occasional accidents or needs help with device.	.....
TOILET TRANSFERS	
10 = Independent with toilet or bedpan, handles clothes, wipes	.....
5 = Needs help for balance, handling clothes or toilet paper	.....
TRANSFERS- CHAIR AND BED	
15 = Independent, including looking of wheel chair, Lifting footrests	.....
10 = Minimum assistance or supervision	.....
5 = Able to sit but needs maximum assistance to transfer	.....
AMBULATION	
15 = Independent for 50 yards. May use assistive device, except for Rolling walker.	.....
10 = With help, 50 yards.	.....
5 = Independent with wheel chair for 50 yards if unable to walk.	.....
STAIR CLIMBING	
10 = Independent. May use assistive device.	.....
5 = Needs help or supervision.	.....
Total: .....	

A score of zero (0) is given in any category in which the patient does not achieve the stated criterion.

**Annex II: SARC-F Questionnaire (Spanish version) for the assessment of sarcopenia.**

**SARC-F Questionnaire**

Date :

Name :

Test administered by :

Component	Question	Scoring	Score
Strength	How much difficulty do you have in lifting and carrying 10 pounds?	None = 0 Some = 1 A lot or unable = 2	
Assistance in walking	How much difficulty do you have walking across a room?	None = 0 Some = 1 A lot, use aids, or unable = 2	
Rise from a chair	How much difficulty do you have transferring from a chair or bed?	None = 0 Some = 1 A lot or unable without help = 2	
Climb stairs	How much difficulty do you have climbing a flight of 10 stairs?	None = 0 Some = 1 A lot or unable = 2	
Falls	How many times have you fallen in the past year?	None = 0 Some = 1 A lot or unable = 2	
TOTAL SCORE			

A score equal to or greater than 4 is predictive of sarcopenia and poor outcomes.

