## Sampling

**Sample and procedure for inclusion of patients in the unexposed cohort.**

In order to carry out an analysis of the new care model (functional recovery programme and patient follow-up through a digital application), the entire simple universe will be included, a complete cohort analysis, with follow-up at 1, 3, 6 and 12 months using a digital toolFollow-up will be carried out at 6 weeks, 4 months and 12 after discharge according to the protocol of the orthogeriatrics unit.

The patient will be given instructions on how to download the application to their mobile device. The application is available in the open repository of mobile applications for public use. Once the app is installed, the patient will be provided with a personal access code that does not include recognisable personal data. This code will be used to connect to the therapeutic plan and to the questionnaires provided by the patient when registering with the Traumatology Service. Only the principal investigator (PI) will have a system of correlation between the code and the patient's personal data, be responsible for its safekeeping.

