**Table II (continuation): Patient follow-up variables**

Variables	Unit of measurement	Type
Functional Capacity and Pain (Oxford Hip Score)	Points (0 to 48)	Quantitative and Qualitative
Falls Risk (STRATIFY Scale)	Points (0 to 5)	Quantitative and Qualitative
Medical complications	0= Fall. 1= Pneumonia. 2= New fractures. 3= Dementia. 4= Acute Myocardial Infarction 5= Pulmonary embolism. 6=Deep vein thrombosis; 7=Death.	Qualitative
Quality of life analysis: questionnaire EQ-5D-5L	Levels (1 to 3125) Points (0 to 100)	Qualitative Quantitative
Abbreviations: RNFC: National Hip Fracture Registry, mFAC: Modified Functional Ambulatory Classificator,		

- **Level of dependency: the Spanish version of the *Barthel Index* will be used (Annex I).** The "*Barthel Index*" provides quantitative information on the level of dependence for activities of daily living by measuring ten activities that are considered basic (441,42). This scale has been used in other studies and shows a direct relationship between high levels of dependency and poor physical health (441). "The Barthel Index has demonstrated good inter-observer reliability, with Kappa indices between 0.47 and 1.00, intra-observer reliability with a Kappa index between 0.84 and 0.97 and internal consistency with a Cronbach's alpha of 0.86-0.92 (39-41).

Test results:

- Values: 0-20 total dependency.
- Values: 21-60 severe dependence.

- Values: 61-90 moderate dependence.
- Values: 91-99 low dependency
- Values: 100 independence.

This scale is administered at 6 weeks, 4 months and 1 year.

- **Sarcopenia assessment: using the SARC-F scale (ANNEX II) (42).**

It is an easily accessible questionnaire, validated in Spanish, which allows the identification of subjects at risk of sarcopenia. The maximum score is 10 points. A score of < 4 points after the test indicates an acceptable state of health, while any score higher than this indicates a risk of sarcopenia (43).

This scale is administered at 6 weeks, 4 months and 1 year.

- **Assessment of functional capacity and specific hip pain: "Oxford Hip Score (OHS)" (ANNEX III)**

It has high repeatability and reliability, with a Cronbach's Alpha value of 0.84 preoperatively, ICC=0.94, and 0.89 at six months and one year (44).

It is a 12-item questionnaire, each item is answered on a five-level Likert-type scale where 4 is the minimum impact and 0 the most unfavourable (45).

Results:

0-19: Severe impact.

20-29: Moderate to severe impact.

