30-39: Mild to moderate impact.

40-48: Satisfactory condition.

This scale is administered at 1, 3, 6 and 12 months.

- **Monitoring of adverse events.**

During the follow-up period, information will be collected on variables derived from post-surgical and medical complications, and falls risk monitoring will be performed.

- **Adverse events. Catalogued in:**

0= Fall.

- 1= Pneumonia.
- 2= New fractures.
- 3= Dementia.
- 4= Acute Myocardial Infarction.
- 5= Pulmonary embolism.
- 6=Deep vein thrombosis.
- 7= Death.

This scale is administered at 6 weeks, 4 months and 1 year.

- **Falls risk scale: STRATIFY scale.**

It can predict which patients are at high risk of falls, with sensitivity values of 92% and specificity of 68% for the elderly population (46).

The total score of the STRATIFY scale is obtained based on the sum of the answers to the five questions, which can take values between zero and five. A score of 0 corresponds to a risk considered low, equal to 1 corresponds to a moderate risk and, finally, greater than or equal to 2 corresponds to a high risk (47).

Question:

1. Patient hospitalised for falls or with episodes of falls during hospitalisation?
2. Restless patient?
3. Are you a patient with visual impairment that affects your daily activity?
4. Patient with a frequent need to use the toilet?
5. Does the patient have a transfer or mobility score of 3 or 4?

However, in the last question, the score is obtained by combining two answers from the modified Barthel index in relation to, respectively, the patient's ability to:

- Transferring from bed to a chair
  - 0: incapable.
  - 1: needs significant assistance.
  - 2: Needs minimal assistance.

3: Independent.

- Level of mobility of the patient:

0: Immobile.

1: Independent with the help of a wheelchair.

2: Use walking aids or walk with the help of a person.

3: Independent.

This scale is administered at 6 weeks, 4 months and 1 year.

- **Quality of life analysis: EQ-5D-5L questionnaire (ANNEX IV) (48).**

It is a self-administered questionnaire divided into two parts, the descriptive system and the Visual Analogue Scale (VAS).

- The descriptive system EQ-5D-5L. describes health status along five dimensions:
  - Mobility.
  - Self-care.
  - Daily activities.
  - Pain/discomfort.
  - Anxiety/depression.

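### The SARC-F falls item looks back one year, so the index fall can add a point at 6 weeks and 4 months and drop out at 1 year, with no change in muscle function

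*Combined protocol and SAP*

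**What the plan says.** Annex II gives the SARC-F as five items. The last asks "How many times have you fallen in the past year" and is scored "None = 0 Some = 1 A lot or unable = 2". It gives no fall counts for the middle and top answers, and no instruction to leave out the fall behind the hip fracture.

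In the Variables section, the SARC-F description says "The maximum score is 10 points" and "This scale is administered at 6 weeks, 4 months and 1 year". Table III lists the same three visits and none at admission. Annex II gives the threshold: "A score equal to or greater than 4 is predictive of sarcopenia and poor outcomes".

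The plan uses two time origins. The Sampling section sets in-person follow-up at "6 weeks, 4 months and 12 after discharge according to the protocol of the orthogeriatrics unit", while the introduction to the second group of variables counts one year from the operation. That introduction also says these variables can be measured only in the 2021 (unexposed) cohort. The sarcopenia item under Specific objectives is accordingly a description of the programme's impact in that cohort alone.

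**The concern.** The item's one-year window covers different periods of the patient's life at each visit. At 6 weeks and 4 months it lies mostly before the fracture and contains the index fall. At 12 months it covers essentially the follow-up year. A fall counted at the first two visits can therefore vanish at the third because time has passed.

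The resulting change is always in the direction of improvement. The 2020 cohort has no SARC-F, so no between-group difference can remove it. There is no admission score to show how much of the early total came from the index fall. A reader of visit-by-visit SARC-F results could credit the programme with a gain that the recall window produced.

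**Working it through.** **1. The plan's own figure.** Five items scored 0 to 2 give 5 × 2 = 10, which matches the stated maximum. Without the falls item, 4 × 2 = 8.

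**2. What the window covers.** Taking visits from discharge and a 365-day window, the share lying after discharge is:
- 6 weeks: 42/365 = 11.5%, leaving 323 days before discharge
- 4 months: 122/365 = 33.4%, leaving 243 days
- 12 months: 365/365 = 100%, leaving 0 days

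The index fall precedes both discharge and surgery. It is inside the window at the first two visits and outside it at a 12-month visit held on time, whichever origin is used.

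**3. One patient.** Assume the fracture came from a fall, there is no other fall in the window, and a single fall is scored as the middle answer. The item then reads 1, 1, 0. If the other four items total 3 throughout, the SARC-F total reads 4, 4, 3. The patient leaves the at-risk group with no change on any muscle-function item.

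**4. How firm the drop at 1 year is.** Days since the fall = 365 − days early + days from fall to discharge. The documents give no fall-to-discharge interval and no visit windows, so the values below are assumptions.

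| Fall to discharge | On time | 7 days early | 14 days early | 30 days early |
|---|---|---|---|---|
| 5 days | 370, out | 363, in | 356, in | 340, in |
| 10 days | 375, out | 368, out | 361, in | 345, in |
| 15 days | 380, out | 373, out | 366, out | 350, in |

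If surgery is the origin, the margin is the fall-to-surgery interval, which is shorter.

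**5. Average shift.** If a share q of patients lose the point, the mean total changes by −q. For an assumed q of 50% to 90%, that is −0.5 to −0.9 points.

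**6. Patients placed to cross the threshold.** These are patients with exactly 3 on the other four items. For an assumed binomial(8, p), P(3) = 56 p³(1 − p)⁵:
- p = 0.3: 25.4%
- p = 0.4: 27.9%
- p = 0.5: 21.9%
- p = 0.6: 12.4%
- p = 0.7: 4.7%
- p = 0.8: 0.9%

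High p is plausible here. Using a walking aid scores 2 on the walking item, and Level 3 of Annex VIII starts patients on a walker or crutches.

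Only those who also lose the point cross. If that is independent of the other items, the false fall in the at-risk proportion is P(3) × q. This runs from 0.9% × 0.5 = about 0.5 percentage points to 27.9% × 0.9 = about 25 percentage points.

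**The case against.** The strongest reply is that the drop is conditional and fragile. A fall is not an eligibility criterion: low-energy fracture appears only as background in the Summary, although polytrauma and metastatic fractures are excluded. Patients who fall again during follow-up can keep the point. The index fall leaves the window by a matter of days, so an early visit or loose recall of the past year brings it back. All of this stands. It means that the size cannot be fixed from the documents, and that the item at 1 year depends partly on scheduling.

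It can also be said that the objective is descriptive, and that the analysis paragraph names no 4-month to 1-year SARC-F contrast. That is correct, so no false-positive rate is attached to the point. But the scale is collected at three visits to describe the programme's impact, and visit-by-visit summaries would carry the same shift. A further reply is that one cohort without a baseline cannot support attribution to the programme in any case. That also stands, and the remedy below does not cure it; it removes only this one directional distortion.

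A reader might infer that the first STRATIFY item has the same flaw, since it asks "Patient hospitalised for falls or with episodes of falls during hospitalisation". The documents do not support this. That item has no one-year window. Read as the index admission, it is yes at all three visits for a patient admitted after a fall. Read as a current admission, it is no at all three for an outpatient. Neither reading produces a drop at 1 year.

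**Conclusion.** The point holds in a limited form. For a patient whose only fall in the window is the index fall, and whose 12-month visit is on time, the SARC-F total drops by 1 of 10 points with no change in muscle function. The drop favours the programme, and nothing in the design offsets it.

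The number of such patients is unknown. Under an assumed binomial for the other items with p from 0.3 to 0.8, about 1% to 28% of patients have exactly 3 on them; those who actually cross the threshold are a subset. A reader might infer that nearly every patient will show a false improvement. New falls, visit timing and the absence of a fall criterion rule that out as a conclusion from the documents.

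The effect is confined to one descriptive specific objective in one cohort. It does not touch the between-cohort comparison of gait.

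A reader might also see a conflict over the threshold, because the Variables section calls scores below 4 acceptable and then says "any score higher than this indicates a risk of sarcopenia", which leaves exactly 4 unclear. This is clerical: Annex II counts 4 as positive.

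**What to change.** Leave the SARC-F as it is, so that its total and threshold remain usable. Add two sentences to the analysis paragraph:

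- Change in SARC-F over visits will also be reported on the four non-fall items (range 0-8), as a sensitivity analysis.
- Falls will be described as new falls since surgery, taken from adverse-event code 0.

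The index fall then contributes nothing to the four-item total at any visit. Code 0 is already collected at 6 weeks, 4 months and 1 year, so no new data are needed. The cost is a small amount of extra tabulation. The downside is that the four-item total has no stated cut-off, so it can show change in score but cannot replace the at-risk proportion. That is why it belongs beside the full score and not in its place.
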